##### 4.2 Accrual, eligibility violations and exclusions from analyses (Enrolled Population)

- a. Number (%) enrolled (i.e. having a signed informed consent form for screening): overall and by month/year. Dates of first and last subject's enrollments. [STEP]
- b. Screen failures: Number (%) by reason. [SCRVIS3]
- c. Number (%) randomized: overall and by month/year. Dates of first and last randomizations. [STEP]
- d. Table: Number (%) randomized by site.
- e. List: Description of violations/deviations of eligibility criteria among subjects randomized: Randomized arm, subject ID, site, age, sex, study treatment dispensed (yes or no), whether in PE Population, subject's study status (completed 28 days, died, or discontinued early from study including reason for discontinuation), category of issue (violation or deviation) and description of issue (site narrative). [DEVTRK]
- f. List: Description of exclusions from analyses among subjects randomized but who did not have study treatment dispensed: Randomized arm, site, subject ID, reason study treatment not dispensed. [Note: The only randomized subjects who will be excluded from all analyses are those subjects who did not have study treatment dispensed].

*All following analyses will be restricted to the ITT Population (or further to the Primary Efficacy Population where noted).*

#### **4.3 Selected characteristics of participants at Day 0 (day of randomization) prior to starting study treatment**

##### **4.3.1 Demographics and other characteristics: (Enrolled population and ITT)**

- a. Age [CASE]
- b. Sex [PATIENT]
- c. Ethnicity [PATIENT]
- d. Race [PATIENT]
- e. Country [CURRENT]

##### **4.3.2 Influenza infection (ITT)**

- a. Site test for influenza used to determine eligibility [SCRVIS3]
- b. Results of influenza diagnostic test at sites (positive or negative) [SCRVIS3]
- c. Influenza type/subtype by local testing at sites [SCRVIS3]
- d. Confirmed influenza infection status (yes or no) [as defined in the protocol] by nasopharyngeal(NP) swab tested by PCR at central virology laboratory [IRCRSLTS]
- e. Confirmed influenza type/subtype by NP swab tested by PCR at central virology laboratory [IRCRSLTS]

##### **4.3.3 Disease and vaccination status (ITT)**

- a. Hours since onset of influenza-like illness to screening (as defined in protocol section 4.3, item 4) [SCRVIS3]

- b. Hours from screening to randomization
- c. Hours from randomization to treatment initiation [SDCOMP1]
- d. Influenza vaccination the season of (and anytime prior to) enrollment
- e. Vital signs: Blood pressure (diastolic and systolic), heart rate, mean arterial pressure, temperature [VITALS2]
- f. Smoking status (current, previous, never)
- g. Anthropometric measurements: weight, height, body mass index [VITALS2]
- h. SaO2 and SaO2 category (<93% vs. ≥93%) [VITALS2]
- i. Presence of fever (≥38°C) [DIARY1]
- j. Symptom score for each of the following symptoms (scored on a 4-point scale: 0=absent, 1=mild, 2=moderate, 3=severe) [DIARY1]
  - Cough
  - Nasal obstruction
  - Sore throat
  - Fatigue
  - Headache
  - Myalgia
  - Feverishness
  - Rhinorrhea
  - Nausea
  - Vomiting
  - Diarrhea
  - Other (as specified by study participant)
- k. Overall symptom score (defined as the sum of scores for the preceding list of symptoms)
- l. Functional status pre-illness (assessed using subjects pre-illness recall of the 10-item domain of Physical Function from the SF-36) [DIARY1]
- m. Functional status on Day 0 (assessed using the 10-item domain of Physical Function from the SF-36) [DIARY1]
- n. Presence of each of the following complications of influenza [EVENTS3]:
  - Sinusitis
  - Otitis media
  - Bronchitis / bronchiolitis
  - Pneumonia
  - Antibiotic use for reason other than above

#### 4.3.4 Virology Measures (ITT and PEP) [team collected swabs]

- a. Viral shedding in nasopharyngeal (NP) swab by qPCR: number (%) <LOD, LOD-<LLOQ, ≥LLOQ, and summary of quantitative values on log10 scale [IRCRSLTS]
- b. Housekeeping (HK) gene levels by qPCR: number (%) <LOD, LOD-<LLOQ, ≥LLOQ-≤ULOQ, >ULOQ, and summary of quantitative values on log10 scale [IRCRSLTS]
- c. Viral shedding in nasopharyngeal (NP) swab by qPCR by housekeeping gene detection [IRCRSLTS]:

- NP virus <LOD: % HK <LOD, % HK LOD-<LLOQ, % HK  $\geq$ LLOQ- $\leq$ ULOQ, % HK >ULOQ
- NP virus LOD-<LLOQ: % HK <LOD, % HK LOD-<LLOQ, % HK  $\geq$ LLOQ- $\leq$ ULOQ, % HK >ULOQ
- NP virus  $\geq$ LLOQ: % HK <LOD, % HK LOD-<LLOQ, % HK  $\geq$ LLOQ- $\leq$ ULOQ, % HK >ULOQ

#### 4.3.5 Virology Measures (ITT and PEP) [self-collected swabs]

- a. Viral shedding in self- collected swabs by qPCR: number (%) <LOD, LOD-<LLOQ,  $\geq$ LLOQ, and summary of quantitative values on  $\log_{10}$  scale [IRCRSLTS]
- b. Cross-tabulation of the viral test results for self- and team-collected swabs on Day 0 swab by whether or not virus was detected at Day 0. Comparison will use first available team-collected swab and the daytime self-collected swab on Day 0.

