##### 4.1 Analysis Populations

All tables and figures will note the analysis population used:

- Enrolled Population includes all subjects who had a signed informed consent form for screening.
- Intention To Treat (ITT) Population includes all subjects who were randomized and who received at least one dose of study drug (as defined in Section 7.2.1 of the protocol).
- Primary Efficacy Population (PEP) includes subjects in the ITT population with influenza infection confirmed in central laboratory testing. Given the virology needed to analyze the primary endpoint, this is defined as having an influenza virus isolated and typed in the qualitative PCR evaluation at Day 0 from central laboratory testing (or Day -1 if Day 0 not available).
- The population for the primary analysis is defined as the subgroup of the PE Population that excludes the subjects who participated in the pilot study (because efficacy results for those subjects were used in selecting the primary endpoint for the study).

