#### **4.10 Evaluation of self-collected samples (PEP and ITT)**

Self-collected NP are collected on Day 0 (prior to treatment initiation), Day 0 evening, Day 1, Day 1 evening, Day 2, Day 2 evening and Day 3. Viral shedding will be assessed using these self-collected swabs by the same assay used for the team collected swabs, i.e., quantitative RT-PCR (reported as  $\log_{10}$  RNA copies/mL).

- a. Completeness of viral shedding results showing number (%) at Day 0, Day 0 evening, Day 1, Day 1 evening, Day 2, Day 2 evening and Day 3 who:
  - had swab taken (i.e. submitted)
  - had qPCR result
  - died prior to visit
  - were lost to follow-up prior to the visit
  - were in follow-up but had missing value
- b. Among subjects with Day 3 qPCR results, number (%) with detectable viral shedding at Day 3. Comparison of randomized arms with associated 95% confidence interval and p-value based on the normal approximation to the binomial distribution. This table can be compared to table 4.8.1a, the primary endpoint, to determine if the self-swabs would have similar treatment effects
  - Repeat analysis in the population for the primary analysis (PEP excluding pilot study) to allow direct comparison with primary endpoint.
- c. Bland-Altman plot showing the agreement between the result from the self-collected swabs and team-collected swabs across all available swabs
- d. Bland-Altman plot showing the agreement between the result from the self-collected swabs and team-collected swabs on Day 0 and Day 3.
- e. Table: Mean, standard deviation, median, min, max, 25% and 75% percentiles of the viral load difference between self-collected swabs and team-collected swabs on Day 0, Day 1, Day 2 and Day 3. P-values comparing the difference based on normal approximation or Wilcoxon signed rank test, as appropriate for the data.
- f. Plots of associations between viral load based on self-collected swabs and viral load based on team-collected swabs on Day 0, Day 1, Day 2 and Day 3. Spearman correlation coefficients, along with their 95% confidence intervals, will be provided. Plots of associations and estimated correlation coefficients will be provided both over all subjects and by strata defined by quartile of the viral load based on team-collected swabs at each time point.

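### In the PEP, the Day 0 self- versus team-swab comparison is biased against the self swab, and the SAP does not say that the unselected ITT version governs

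*SAP*

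**What the plan says.** The SAP compares the two collection methods at Day 0 in two places.

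- Section 4.3.5, whose heading names both ITT and PEP, plans at item b a "Cross-tabulation of the viral test results for self- and team-collected swabs on Day 0 swab", split by detection of virus. On which specimens are paired, it says: "Comparison will use first available team-collected swab and the daytime self-collected swab on Day 0".
- Section 4.10, also for PEP and ITT, includes Day 0 in an agreement plot over all available swabs (item c), in a "Bland-Altman plot showing the agreement between the result from the self-collected swabs and team-collected swabs on Day 0 and Day 3" (item d), in self-minus-team load differences with p-values (item e) and in Spearman correlations (item f).

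The PEP is the part of the ITT with centrally confirmed influenza, and SAP 4.1 says "this is defined as having an influenza virus isolated and typed in the qualitative PCR evaluation at Day 0 from central laboratory testing" (Day -1 if Day 0 is missing). SAP 4.3.2d ties confirmed status to a specimen: "by nasopharyngeal(NP) swab tested by PCR at central virology laboratory". SAP 4.3.4 places the NP results under team-collected swabs, and protocol Table 4 lists the NP swab separately from self-collection.

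The ITT (SAP 4.1) requires only randomization and one dose. Entry to the trial rests on a site test, rapid antigen or PCR (protocol 4.4).

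**The concern.** Secondary objective 4 is the comparison of self-collected with team-collected samples. The protocol (3.1 and 7.3.4.5) says that if self-collection gives the same quantitative information, future studies could sample more often with fewer clinic visits. A deficit created by the choice of population would argue wrongly against that.

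The PEP keeps a subject whose team swab is positive and self swab negative. It drops a subject whose team swab is negative and self swab positive. Agreement is then judged in a set selected on one of the two measurements. The same selection reaches the Day 0 load differences in 4.10e, which are tested.

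Day 0 carries much of the evidence. Protocol Table 4 schedules team swabs on Days 0, 3 and 7 and self swabs on Days 0 to 3, so scheduled pairs exist only on Days 0 and 3. About half of the pairs in 4.10c are therefore Day 0 pairs. The SAP gives no caution about the PEP version and does not say which population answers the objective.

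**Working it through.** **Inputs.** The documents state no power, agreement figure, Day 0 sensitivity or within-subject correlation for this comparison, so there is no plan figure to reproduce. The sensitivities, correlations, load models and pair count below are assumptions. The 560 is the planned number randomized, used for illustration as if all were infected.

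**Step 1: detection, closed form.** Let both swabs have the same sensitivity s, with correlation r between the two detections in a subject.

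- P(both positive) = s² + r·s(1-s)
- P(team+, self-) = P(team-, self+) = s - P(both positive), so the unselected table is balanced.
- Given team+, P(self+) = s + r(1-s), so the spurious deficit is (1-s)(1-r).

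Example with 560 infected, s = 0.90, r = 0:

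- Both positive: 560 × 0.81 = 453.6. Each discordant cell: 560 × 0.09 = 50.4.
- Without selection: team 90%, self 90%, difference 0.
- Selected on team+: 504 subjects, team 100%, self 453.6/504 = 90%, difference -10 points. The 50.4 self-only positives are gone.

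Other values: s = 0.80, r = 0 gives 0.20 × 1 = 20 points; s = 0.90, r = 0.6 gives 0.10 × 0.4 = 4 points; s = 0.98, r = 0.6 gives 0.02 × 0.4 = 0.8 points.

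**Step 2: detection, load model.** Two swabs from one subject at one visit tend to miss together when load is low, so r = 0 is unlikely. Assume true log10 load with mean 5 or 6, between-subject SD 1.5 or 2.0, swab-to-swab SD 0.7 or 1.2, and LOD 3. Then s = Φ[(mean - 3)/√(between² + swab²)], and r follows from simulation (2 million pairs per setting). The two ends of the eight settings are:

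| Mean | Between SD | Swab SD | s | r | Deficit (1-s)(1-r) |
|---|---|---|---|---|---|
| 6 | 1.5 | 0.7 | Φ(1.81) = 0.965 | 0.47 | 0.035 × 0.53 = 1.9 points |
| 5 | 2.0 | 1.2 | Φ(0.86) = 0.804 | 0.49 | 0.196 × 0.51 = 10.0 points |

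**Step 3: two assays on the team swab.** PEP entry uses the qualitative typing PCR; the comparison uses qPCR. In a separate model (mean 5, between-subject SD 1.5, swab SD 0.5 to 1.5, LOD 2.5) each reading was given assay SD 0.3 log10. Team+/self- was then 2.05% to 8.63% of the PEP and team-/self+ was 0.88% to 1.35%. The team-negative row is not empty, but the imbalance keeps its direction.

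**Step 4: load difference, self minus team.** Over the eight settings in step 2, selecting on team above LOD:

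| Handling of self-swab non-detects | Spurious mean difference (log10) |
|---|---|
| Set to the LOD | about -0.01 to -0.13 |
| Only pairs detected on both swabs | about 0 |

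With an assumed 460 pairs and non-detects set to the LOD, the standard error is about 0.04 to 0.08. For mean 5, between-subject SD 1.5, swab SD 1.2 the difference has SD 1.55, so SE = 1.55/√460 = 0.072, and a bias of -0.129 is 1.8 standard errors. At the favourable end (mean 6, SD 1.5, swab SD 0.7) it is -0.015/0.045, about 0.3.

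**Step 5: symmetric alternatives.** In the same simulations the expected difference was about 0 both without selection and when subjects were kept if either swab was positive.

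**The case against.** Much of the case on the other side stands.

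- *The sound version is already planned.* Both SAP sections also run in the ITT, which is not selected on the central swab. A reader might infer that the comparison is made only in the biased population; the section headings contradict that. What remains missing is a statement of which version governs.
- *The self swab need not look worse.* A reader might infer that it can only do worse in the PEP. That is too absolute. Qualitative PCR and qPCR can disagree, SAP 4.8.2d treats detectable Day 0 load as a further subset, and the self swab could tie at 100%.
- *The PEP table is a legitimate quantity.* It is essentially the team-positive row of the ITT table. That is true, but it is not agreement, and it is not labelled as conditional.
- *Nothing is decided by it.* SAP 4.3.5b has no test, and no agreement margin or decision rule is set. However, 4.10e does attach p-values, and in the PEP its null value is not what equal swabs would produce unless only doubly detected pairs are used.
- *The size cannot be established.* The documents give no sensitivity or correlation, and SAP 4.10c-e does not say how results below LOD enter. The load bias is therefore conditional on that handling.

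One link is inferred: SAP 4.1 does not name the specimen behind the central Day 0 PCR. The reading rests on 4.3.2d and 4.3.4. SAP 4.10 also loosely calls the self-collected samples NP, which is a further reason to state the specimen.

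**Conclusion.** The concern holds for the PEP version of the Day 0 comparison. Selection on the team swab biases it against the self swab when the two perform equally. Under the step 2 models the detection deficit is about 2 to 10 points. It would be below 1 point if sensitivity and correlation were both high, and larger if misses were independent and sensitivity low. The load difference is biased by about -0.01 to -0.13 log10 or by about 0, depending on a non-detect rule that the SAP does not give. All these sizes rest on assumed inputs; the direction follows from the SAP's definitions.

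The documents do not support a wider reading. The ITT version is free of this selection, Day 3 pairs are not selected on either Day 3 swab, and the primary endpoint and the treatment comparisons are untouched. The defect is an unranked pair of answers to secondary objective 4, one of them biased and tested.

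**What to change.** 1. In SAP 4.3.5b, and for Day 0 in 4.10c-f, name the ITT (all subjects with paired Day 0 swabs) as the population for self versus team agreement, and report both discordant cells.
2. If an infected-only set is wanted, define it as virus detected at Day 0 in either the team or the self swab.
3. If the PEP table is kept, label it as self-swab positivity among team-swab positives and attach no agreement p-value to it.
4. State how results below LOD enter 4.10c-e, and name in 4.1 the specimen that confirms infection.
5. Keep the PEP for Day 3 pairs and for the self-swab treatment effect in 4.10b.

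The cost is SAP wording and at most one population flag, with no new data. The downside is that the ITT includes some uninfected subjects. They add double-negative pairs, which raise overall percent agreement but do not distort the discordant cells.

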#### 4.4 Study status of participants and loss to follow-up (ITT)

- a. Died prior to Day 28 evaluation [DEATH2]
- b. Lost to follow-up before completing Day 28 evaluation (with subcategories showing reason for loss) [OFFSDY2]
- c. Completed Day 28 evaluation [OFFSDY2]
- d. List: Randomized arm, days from randomization to last study visit, site, subject ID, protocol version, age, sex, confirmed influenza infection status, days from randomization to last contact, text reason for off study (sort by randomized arm, day of last study visit, subject ID). [OFFSDY2]
- e. Figure: Kaplan-Meier plot (with log rank test comparing randomized arms) of time from randomization to last study visit prior to loss to follow-up (censoring at 28 days if completed Day 28 visit or died before 28 days). [OFFSDY2]

#### 4.5 Study treatment [SDCOMP1] (ITT)

- a. Number of days with all study drug reported as taken : number (%) in following categories
  - 5 days (i.e. completed 5 days)
  - Partial course (i.e. did not complete 5 days) : 0 day to 5 days
- b. List: Reasons for receiving the partial course of treatment or not receiving full planned first course of treatment: randomized arm, number of days with all study drug reported as taken, site, subject ID, influenza type/subtype by central lab testing, reason for not receiving full planned course of treatment.
 

List of subjects who were randomized properly but received wrong study treatment: randomized arm, subject ID, site, age, sex, reasons for not receiving the correct treatment as assigned.

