9.3 Subject Populations

Safety Population: The Safety Population will consist of all participants who are randomized and received at least one dose of the study drug. For interim reviews, this will be limited to data entered into the electronic database up to the cut-off date.

Intention to Treat (ITT) Population: The ITT will be the same as the Safety Population.

Primary Efficacy Population: The Primary Efficacy Population will consist of all randomized (as defined in Section 3.2) subjects with confirmed influenza (as defined in Section 7.3.4, not site diagnostics for influenza). Primary efficacy analyses will be based on this subject population.

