## 1 General analysis considerations

Unless otherwise specified, data summaries and analyses will be presented overall and by randomized arm.

To help protect participant confidentiality, listings of individual patient level data will be minimized as much as possible. Dates will also not be presented in listings; instead, for example, listings will present details as days since randomization.

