#### 4 Analysis Plan

Unless otherwise stated, all tables and figures will show results by randomized arms.

Throughout this analysis plan, annotations in square brackets ([XXX]) provide the source table/view names and, in some cases, target fields in the IRC004 database.

Per protocol, at study entry, results from laboratory tests obtained for clinical indications within 24 hours before randomization may be used if available.

Unless otherwise stated, data will be presented in tables. For tables with categorical variables, the number (%) will be presented. For tables with continuous variables, the mean, standard deviation, median, 25th and 75th percentiles, min and max will be presented. The number with missing values will also be shown. In calculation of percentages, subjects with missing data will not be included in the denominator. Data presented as listings or figures noted.

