## 4.7 Safety Analysis

### 4.7.1 Serious Adverse Events (Enrolled population and ITT)

- a. Enrolled Population: Number (%) of subjects with an SAE by MedDRA System Organ Class (SOC) and Preferred Term (PT); number (%) of subjects with any SAE. This table will include all SAEs, irrespective of time from randomization to the date of onset of the SAE (i.e. including any SAEs reported before randomization or after 28 days).
  - Table repeated to show total number of SAEs (i.e. allowing a subject to be represented more than once per row, SOC header, and in total numbers).
  - ITT Population: Number (%) of subjects with an SAE by MedDRA System Organ Class (SOC) and Preferred Term (PT); number (%) of subjects with any SAE through to the date of the Day 28 visit (or death on/before 28 days).
  - Table repeated to show total number of SAEs (i.e. allowing a subject to be represented more than once per row, SOC header, and in total numbers).
- b. Enrolled Population: List of SAEs: Randomized arm, days from randomization to first SAE experienced by a subject, subject ID, site, confirmed influenza infection status, days from randomization to the date of the SAE, days from first and from last dose of study treatment to the date of SAE, SAE (MedDRA SOC and PT, and verbatim description), severity grade, relatedness to study intervention, outcome (e.g. died/resolved/ongoing) (sort by randomized arm, days from randomization to first SAE, subject ID, and, if a subject has multiple SAEs, days from randomization to SAE).

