#### 4.7.2 Adverse Events (Enrolled population, and ITT)

- a. Enrolled Population: Number (%) of subjects with an AE (as defined above) by MedDRA System Organ Class (SOC) and Preferred Term (PT); number (%) of subjects with all AEs irrespective of time since randomization (i.e. including any reported before randomization or after Day 28).
  - Table repeated to show total number of AEs (i.e. allowing a subject to be represented more than once per row, SOC header, and in total numbers).
- b. ITT Population: Number (%) of subjects with an AE (as defined above) by MedDRA System Organ Class (SOC) and Preferred Term (PT); number (%) of subjects with all AEs from Day 0 to Day 28.
  - Table repeated to show total number of AEs (i.e. allowing a subject to be represented more than once per row, SOC header, and in total numbers).
- c. ITT Population: Number (%) of subjects with an AE (as defined above) by MedDRA System Organ Class (SOC) and Preferred Term (PT); number (%) of subjects with all related AEs (definitely related, probably related, possibly related) from Day 0 to Day 28.
  - Table repeated to show total number of AEs (i.e. allowing a subject to be represented more than once per row, SOC header, and in total numbers).
- d. Enrolled Population: List of AEs: Randomized arm, days from randomization to first AE experienced by a subject, subject ID, site, confirmed influenza infection status, days from randomization to AE, days from last dose of study treatment, AE (MedDRA SOC and PT, and verbatim description), severity grade, relatedness to study intervention, outcome, e.g., died/resolved/ongoing, sorted by randomized arm, days from randomization to first AE, subject ID, and, if a subject has multiple AEs, days from randomization to AE.

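### SAP 4.7 shows adverse events by randomized arm and records no treatment received, so an event in a subject given the wrong treatment appears under a treatment not taken (minor)

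*SAP*

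**What the plan says.** Three parts of the SAP bear on this.

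- **Default grouping.** SAP 1 says: "Unless otherwise specified, data summaries and analyses will be presented overall and by randomized arm". SAP 4 repeats it for outputs: "Unless otherwise stated, all tables and figures will show results by randomized arms".
- **Wrong treatment.** SAP 4.5 plans a "List of subjects who were randomized properly but received wrong study treatment". Its fields are randomized arm, subject ID, site, age, sex and the reason. The treatment taken is not among them.
- **Safety outputs.** SAP 4.7.1 and 4.7.2 use the Enrolled and ITT populations and state no other grouping. The listings start from the randomized arm and are sorted by it. 4.7.1b begins "Enrolled Population: List of SAEs: Randomized arm, days from randomization to first SAE experienced by a subject" and 4.7.2d begins "Enrolled Population: List of AEs: Randomized arm, days from randomization to first AE experienced by a subject". Neither has a treatment-received field.

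On populations, Protocol 9.3 says: "The Safety Population will consist of all participants who are randomized and received at least one dose of the study drug". It then makes the ITT population identical to that set. SAP 4.1 defines ITT in the same terms and defines no separate safety population.

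**The concern.** For efficacy, the randomized arm is the right label, because it preserves the comparison that randomization created. A safety table describes what happened after exposure, so its label should follow the drug taken. Here the plan expects that the two may differ for some subjects, but it does not use that information where it would matter.

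The route to such an error is ordinary. Protocol 6.3.2.2 has the system issue a kit number that is passed to a pharmacist or designee, at up to about 50 sites. Under Protocol 5.2 the active and placebo capsules look the same, so a subject would not notice the wrong kit.

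What is at stake is the reading of a few events. Protocol 8.3.1 leaves out most grade 1-3 events that are known oseltamivir effects or influenza symptoms. The recorded events are therefore weighted towards unusual, clinically significant and serious ones, whose counts are likely to be low. An SAE, or an AE judged related (4.7.2c), that followed oseltamivir could be displayed in the placebo column, or the reverse.

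**Working it through.** **1. What the sections give when followed literally.** Take a subject randomized to placebo who was given an oseltamivir kit and had an SAE.

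- SAP 4.5: listed under placebo with a reason; treatment taken not shown.
- SAP 4.7.1 table: counted under placebo, because no statement there overrides SAP 1 and 4.
- SAP 4.7.1b listing: shown under placebo, with days from first and last dose but not which treatment.
- No section links the 4.5 list to the 4.7 outputs, and no table by treatment received is planned.

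**2. Inputs for the size.** 560 randomized 1:1 (SAP Protocol Summary) gives 560/2 = 280 per arm. The documents give no wrong-treatment rate and no expected event rates, so both are assumed below. The plan states no figure on this point to reproduce.

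**3. Pooled rates.** Let a share m of each arm take the other treatment, and let p_O and p_P be the event risks by treatment received.

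- Risk in the oseltamivir arm as randomized: (1-m)p_O + m p_P
- Risk in the placebo arm as randomized: (1-m)p_P + m p_O
- Difference: (1-2m)(p_O - p_P)

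With assumed risks of 5% and 2%, a true difference of 3.0 points:

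| Wrong treatment per arm | m | 1-2m | Difference shown (points) |
|---|---|---|---|
| 1 | 0.4% | 0.993 | 2.98 |
| 3 | 1.1% | 0.979 | 2.94 |
| 6 | 2.1% | 0.957 | 2.87 |
| 14 | 5% | 0.90 | 2.70 |
| 28 | 10% | 0.80 | 2.40 |

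An assumed rate of 1-3% is 2.8 to 8.4 subjects per arm. Across the rows near 1-2%, the difference shown falls by 0.06 to 0.13 points.

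**4. A single rare event.** One misplaced subject moves 1/280 = 0.36 points out of one column and into the other. If the trial had one SAE, the table would read 0 v 1 instead of 1 v 0. If SAE risk is unrelated to the dispensing error, the chance that a lone SAE falls in a wrong-treatment subject is about m, so 1-3% at the assumed rate.

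**The case against.** Much of the case on the other side stands.

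- **No protocol rule was dropped.** A reader might infer that the protocol defines safety by exposure and that the SAP failed to carry this over. Protocol 9.3 does not support that. It sets membership only, gives no rule for grouping by treatment received, and equates ITT with the Safety Population. The SAP's ITT is the same set.
- **No inference is reversed.** It is tempting to say that one misplaced event could overturn the safety comparison. SAP 4.7 specifies counts, percentages and listings, with no test, interval or decision rule. A count of 1 v 0 supports no conclusion either way. Protocol 8.3.1 itself expects the study to add little to what is known of oseltamivir safety.
- **Relatedness is not a judgement on a named drug.** One might read 4.7.2c as tying a causal judgement to a drug the subject did not take. The SAP refers to relatedness to the study intervention, and, except after unblinding, the investigator assesses a masked treatment. The column label would be wrong, but the judgement would not.
- **Cases can be traced.** The 4.5 list and the 4.7 listings all carry subject ID and randomized arm, and there are only two arms, so a reader could match them and infer the treatment. This is only a partial answer. No such matching is planned, and the inference fails for a subject who took capsules from both treatments.
- **Moving events between columns has a side effect.** Deaths and inpatient hospitalizations are SAEs under Protocol 8.2 and are also analysed by arm in SAP 4.6. Relabelling only 4.7 could place one event under different arms in the two sections. The fix must deal with this.

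The gap itself is not answered: as written, the plan puts such a subject's events under a treatment not taken.

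**Conclusion.** The point holds as a minor gap in the SAP's safety presentation. It needs at least one subject who took the wrong treatment and had a recorded event. The documents do not say how likely that is, and the rates used above are assumptions. At rates around 1-2% the effect on pooled rates is negligible. It matters only for reading rare SAEs or related AEs in descriptive tables, where a single event is visible. The overall columns are unaffected, and if nobody received the wrong treatment, nothing changes. The SAP's introductory pages were not in the text available, so a grouping rule stated there could not be checked.

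**What to change.** - **SAP 4.7, tables.** State that post-dose AE and SAE tables for the ITT population are presented by treatment actually received, with any oseltamivir dose counting as oseltamivir. At the least, add these as supportive tables beside those by randomized arm.
- **SAP 4.5, 4.7.1b and 4.7.2d, listings.** Add a treatment-received field and a wrong-treatment flag, and keep the randomized arm.
- **Efficacy and SAP 4.6.** Keep efficacy analyses and the mortality and hospitalization analyses by randomized arm. Add a footnote wherever a 4.6 event falls under a different arm in 4.7.

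The rule is best fixed before unblinding, so that the placement of a known event is not chosen afterwards.

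The cost is a few lines of SAP text and one derived variable. Denominators and event placement may differ slightly between 4.6 and 4.7, which the footnote explains.
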